4.2 Objectives and Hypotheses

Phase 1: Design and Development of the Virtual Reality Experience

1. Work with an interdisciplinary team to collaboratively develop an engaging prototype (V1.0) that models the MRI environment and experience at BCCH.

Phase 2: Technology Evaluation and Comparative Assessment

2. Evaluate the effectiveness in pre-procedural preparation through a comparative assessment against other modes of delivery currently offered at BCCH – including pre-procedural instructional booklet, and mock MRI with CLS.
 - a. *Hypothesis:* There will be differences in outcomes between the virtual reality group and the booklet group.
 - b. *Hypothesis:* There will be no difference in outcomes between the mock MRI and virtual reality simulation groups.
 - c. *Hypothesis:* Children will prefer the virtual reality and simulation exercises to booklet preparation.

Phase 3: Economic Evaluation and Impact Modeling

3. Evaluate costs and benefits of the VR solution and status quo; and conduct economic modelling on the prospective impact of operational integration.

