4.5 Phase 3: Economic Evaluation and Impact Modelling

Objective 3: Evaluate costs and benefits of the VR solution and status quo; and conduct economic modelling on the prospective impact of operational integration.

The final phase of this project seeks to answer the following questions:

- What are the current costs of Sedated and Non-Sedated MRI procedures at BC Children's Hospital? (including hospital/health systems costs and average economic burden on patients and families).
- What is the total cost avoidance and opportunity-cost savings in converting a sedated case to a non-sedated case?
- What is the cost-effectiveness of current interventional strategies?
- What is the potential incremental cost-effectiveness ratio of the VR simulation compared to the status quo model (given known limitations)?
- What are the relative impacts to patient/families, hospital, and the health system at large of the various interventions?

The economic modelling will be conducted in a series of stages: (1) cost analysis, (2) outcomes (benefits) analysis, and (3) multi-level modelling of cost-effectiveness (from patient/family, hospital, health systems perspectives).

Stage 1: Cost Analysis

Costs will be analyzed from the perspective of the program implementer (hospital) and estimated for patients/families, and will be reported in Canadian dollars.

For hospital costs, we will analyze administrative/operational costs and clinical volume to present an average case cost for the status quo model and intervention groups. Program costs will be categorized into capital and operational costs, and segmented as technology, administrative, operational and resource costs:

- Technology costs will include hardware devices, technology-related consumables, and technical support. Capital costs for the media development will be measured for the purposes of a parallel return on investment (ROI) analysis, but will be excluded from operational cost-effectiveness analysis (CEA), with the assumption that in many scenarios existing media may be available for use. Multiple CEA models will be produced at varying media costs thresholds, simulating custom content development (using actual incurred/in-kind costs) as well as estimated costs for 'off-the-shelf' media procurement (based on current state market pricing).

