Outcomes will be reported at both the hospital and patient/family perspective, based on the data gathered in Phase 2 (**Table 4**); this includes the predictive non-sedation rates, length of hospital stay, and reductions in anxiety from the patient and family perspectives.

Stage 3: Multi-Level Cost-Effectiveness Modelling

Cost-Effectiveness will be modelled across the various scenarios identified and from multiple perspectives (i.e. hospital, patient/family). To support decision-making, we will determine the **incremental cost-effectiveness ratio (ICER)** of the intervention versus the control. ICER is a statistic used to summarise the cost-effectiveness, and is defined by the difference in cost between two possible interventions, divided by the difference in their effect; this represents the average incremental cost associated with 1 additional unit of the measure of effect. For our study, we will measure ICERS for multiple outcome variables that are measured in Phase 2.

Uncertainty Analysis

We expect the number of users, the average amount of consumables and equipment used, and the amount spent on promotional costs to fluctuate. Therefore, we will conduct a probabilistic uncertainty analysis around these program variables to determine sensitivity and what the expected range of cost-effectiveness might be. These values and distribution for the uncertainty analysis will be selected based on one-year data.

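### The Phase 3 ICERs are planned against a comparator not mapped to either comparison arm, and if hypothesis 2b is true the ratio of VR to mock MRI is unstable

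*Combined protocol and SAP*

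**What the plan says.** Section 4.5, Stage 3, plans an ICER "of the intervention versus the control. ICER is a statistic used to summarise the cost-effectiveness". It defines the ratio for a pair of options: it "is defined by the difference in cost between two possible interventions, divided by the difference in their effect". It plans several such ratios: "For our study, we will measure ICERS for multiple outcome variables that are measured in Phase 2". It also says: "Cost-Effectiveness will be modelled across the various scenarios identified and from multiple perspectives".

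The question list at the start of section 4.5 words the comparator differently: "What is the potential incremental cost-effectiveness ratio of the VR simulation compared to the status quo model (given known limitations".

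Section 4.2 sets VR "against other modes of delivery currently offered at BCCH – including pre-procedural instructional booklet, and mock MRI with CLS". Section 4.4 allocates children to VR, mock MRI or booklet, and none of these is labelled the control. Hypothesis 2b in section 4.2 reads: "There will be no difference in outcomes between the mock MRI and virtual reality simulation groups". It gives no equivalence margin.

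The uncertainty analysis at the end of section 4.5 varies the number of users, consumables and equipment, and promotional spending. The documents mention no dominance ordering, no net benefit, and no rule for an effect difference close to zero.

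**The concern.** Two gaps combine.

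First, the comparator is open. The control or status quo could be the booklet, the mock MRI with a Child Life Specialist, or a mix. The comparison-group table in section 4.4 shows that these use different resources: a research assistant runs the booklet session and a Child Life Specialist runs the mock MRI. VR could plausibly cost more and gain effect against one, and save money at equal effect against the other. If the choice is left open, it can be made after the results are known. A two-option ratio also gives no rule for ranking three options.

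Second, if the comparator is mock MRI, the plan's own hypothesis puts the expected denominator at zero. The sign and size of the ratio would then be set largely by chance, in the very scenario the sponsor expects. The sign alone does not help the reader, because a negative ICER arises both when VR is cheaper and better and when it is dearer and worse. At stake is the conclusion of the economic phase about adopting VR. The Phase 2 comparison of the arms is not affected.

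**Working it through.** **Inputs.** Phase 3 states no cost, effect or ICER, so there is no planned figure to reproduce there.
- Children per arm: 31 (section 4.4). With the 10% dropout allowance in the sample size paragraph, 31 × 0.9 = 27.9, about 28.
- Anchor for the pass rate: 283/344 = 82.3%, which matches the 82% conversion stated in section 3.0. These were referred patients, so the trial rate is unknown and 50–95% is shown.
- Effect difference under hypothesis 2b: zero, so both arms get the same true pass rate p.
- Effect unit: pass/fail, an assumption made for this check.

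**Distribution of the denominator.** Let X and Y be the passes in the VR and mock MRI arms, independent Binomial(n, p). Then ICER = ΔC/ΔE with ΔE = (X − Y)/n. It is undefined when X = Y, with probability Σₖ P(X = k)², and each sign of ΔE has probability (1 − P(X = Y))/2.

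| n per arm | p | ΔE = 0 (undefined) | each sign of ΔE |
|---|---|---|---|
| 31 | 50% | 10.1% | 45.0% |
| 31 | 82% | 13.2% | 43.4% |
| 31 | 95% | 24.2% | 37.9% |
| 28 | 50% | 10.6% | 44.7% |
| 28 | 82% | 13.9% | 43.0% |
| 28 | 95% | 25.6% | 37.2% |

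At 82% and n = 31, the two arms differ by at most one child in 38.2% of trials. The standard error of ΔE is √(2 × 0.82 × 0.18/31) = 0.098, so the 95% half-width is 1.96 × 0.098 = 0.191, or 19 points.

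**If 2b is not exactly true.** With mock MRI at 82.3% and VR 5 points better (n = 31), ΔE still has the wrong sign in 23% of trials and is zero in 12%.

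**Against the booklet.** Assume a true gap of 20 points, at rates from 30% against 50% up to 70% against 90%. With n = 31, ΔE has the wrong sign in 1–4% of trials and is zero in 2–3%. With n = 28 these are 2–5% and 2–3%. The instability therefore belongs mainly to the mock MRI comparison.

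**What one child does to the ratio.** The documents give no costs, so assume that VR is $100 cheaper per child (ΔC = −100) and that an extra pass is valued at λ = $1,000. Net benefit is λΔE − ΔC.

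| VR minus mock MRI, n = 31 | ICER | Net benefit |
|---|---|---|
| one more pass | −100/(1/31) = −$3,100 | 32 + 100 = $132 |
| tie | undefined | $100 |
| one fewer pass | −100/(−1/31) = +$3,100 | −32 + 100 = $68 |

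With assumed cost differences of −$50 to −$200, the one-child ICER runs from ±$1,550 to ±$6,200. If VR were instead $100 dearer with one fewer pass, the ICER would be 100/(−1/31) = −$3,100. That is the same number as in the first row, with the opposite meaning.

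Net benefit passes smoothly through zero effect, but a point estimate of it still hides sampling error. At λ = $1,000 the 95% half-width from the effect alone is 1,000 × 0.191 = $191 around $100, or −$91 to $291. This is why the effect must enter the uncertainty analysis.

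**The case against.** The strongest reply is that this is a decision model, so its comparator need not be a trial arm. Objective 3, the Phase 3 questions and key question 3 all speak of the status quo, and the control in Stage 3 most naturally means the same thing. A mixed current pathway is a legitimate comparator. That stands as far as it goes: a comparator is named. What the documents do not give is its composition or its link to the two arms that supply the effect data.

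Three stronger readings are tempting, and the documents do not support them.
- A reader might infer that only one ICER is planned. Stage 3 plans ratios for several outcomes, scenarios and perspectives. What is single is the comparison pair.
- A reader might infer that key question 2 will be answered from this ratio alone. Section 4.5 lists four other economic questions, a parallel return-on-investment analysis, average case costs by group, and a separate outcomes report. Much of what is needed to show cost and effect differences is already planned.
- A reader might infer that VR is in fact dominated by one of the other strategies. The documents give no costs, so this is only possible.

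The arithmetic also has limits. Length of stay and anxiety are further effect measures. The probability of an exact tie does not carry over to minutes of stay, although 2b speaks of outcomes in general and so still implies a denominator near zero. The 82% figure is conversion to non-sedated MRI in referred patients, whereas the trial outcome is a head-motion threshold in openly recruited children. The simulator pass rate from Table 2 is (283 + 8)/344 = 84.6%, inside the range shown.

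Finally, the plan calls its ICER potential and subject to known limitations, and some of the remedy is reporting preference. That argues for a modest priority. It does not make the ratio against mock MRI interpretable.

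**Conclusion.** The point holds in this form. The ICERs are defined for one pair whose comparator is named in two ways and mapped to neither comparison arm. If 2b is true, the ratio against mock MRI is undefined in 10–26% of trials, and its denominator takes each sign in 37–45% (13% and 43% at 82% and 31 per arm). These figures assume pass/fail as the effect, independent arms, equal true pass rates of 50–95% and 28–31 children per arm. The dollar figures are illustrations only. The planned uncertainty analysis would not reveal the problem, because it leaves the effects fixed. This is an inexpensive improvement to the economic phase that should be made before the costs and effects are compared.

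**What to change.** In section 4.5, Stage 3:
1. Replace the two-option comparison with an incremental analysis of booklet, VR and mock MRI. Order them by cost, remove dominated and extendedly dominated options, and give ICERs only between adjacent remaining options. If a mixed status quo is also modelled, state its composition and how the arms feed into it.
2. For VR versus booklet and VR versus mock MRI, report the cost difference and effect difference side by side. Add incremental net benefit over a stated range of values per additional child predicted to avoid sedation. Do not give a bare ratio against mock MRI.
3. Add sampling error of the Phase 2 effects to the probabilistic uncertainty analysis, and show the cost-effectiveness plane.

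The cost is some rewording, slightly more modelling, and the need to choose and justify a range of values per child, which the documents do not supply. No new data collection is needed.

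### The Phase 3 uncertainty analysis carries no sampling error from the Phase 2 effects into the cost-effectiveness ratio, so its stated range will be too narrow

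*Combined protocol and SAP*

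**What the plan says.** Section 4.5 (Stage 3) defines the ICER as a cost difference over an effect difference and adds: "For our study, we will measure ICERS for multiple outcome variables that are measured in Phase 2". Stage 2 names the outcomes: "this includes the predictive non-sedation rates, length of hospital stay, and reductions in anxiety from the patient and family perspectives". Phase 2 times also enter the cost side, because the time-driven costing takes its task times from Phase 2 length-of-stay data and process mapping.

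The Uncertainty Analysis paragraph has three sentences. The first lists what may vary: "We expect the number of users, the average amount of consumables and equipment used, and the amount spent on promotional costs to fluctuate". The second sets the scope: "we will conduct a probabilistic uncertainty analysis around these program variables to determine sensitivity and what the expected range of cost-effectiveness might be". The third gives the source: "These values and distribution for the uncertainty analysis will be selected based on one-year data".

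The other variation planned in section 4.5 is in media cost, in patient and family cost scenarios, and in perspective. The Phase 2 analysis text in section 4.4 plans no interval for the pass-rate difference and no link to Phase 3.

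The ratio is described as being "of the intervention versus the control", and among the Phase 3 questions as VR against the status quo model. Neither term is tied to a Phase 2 arm. Section 4.2 lists both the booklet and the mock MRI as current practice.

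**The concern.** An ICER has two uncertain parts. The three items the plan varies are cost or volume inputs. The denominator comes from a small comparison, and the plan gives it no distribution. One year of operating data can describe volumes and spending, but it does not describe the sampling error of a difference between two arms of about 31 children.

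The plan offers the ICER as an aid to decisions. Section 3.0 treats the economic assessment as a core component of the project, and section 4.2 makes it a numbered objective. A range that reflects cost and volume alone would look firmer than the Phase 2 data allow. The problem is sharpest against mock MRI, where section 4.2 expects no difference in outcomes: the denominator is then expected to be near zero, and a cost-only analysis would give no warning of it. Participants and the Phase 2 results themselves are not affected.

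**Working it through.** Phase 3 states no numerical result to reproduce. The plan figure that matters is 31 children per arm (section 4.4), or about 28 after 10% drop-out (0.9 × 31 = 27.9). The power statement behind the total of 93 omits the within-child correlation, so 93 cannot be reproduced uniquely. The point does not depend on it.

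**Inputs for the illustration**
- 82%: children converted to a non-sedated MRI after simulation, 283/344 (section 3.0, Table 2).
- 62%: assumed, reading the 20% in the power statement as 20 points.
- Neither is the Phase 2 endpoint, which is a 3 mm head-motion threshold in openly recruited children.

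**Step 1. Sampling error of the denominator**

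SE = √[(p₁q₁ + p₂q₂)/n]
- n = 31: √[(0.1476 + 0.2356)/31] = 0.111; 95% CI 0.20 ± 1.96 × 0.111 = -0.018 to 0.418.
- n = 28: SE 0.117; 95% CI -0.029 to 0.429.

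If the 20% is instead relative to the 50% to 75% sedation rates in section 3.0, then at 31 per arm:
- Sedation 50% to 40% (pass 60% v 50%): SE 0.126; 95% CI -15 to 35 points.
- Sedation 75% to 60% (pass 40% v 25%): SE 0.117; 95% CI -8 to 38 points.

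All of these intervals include zero.

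**Step 2. Direction**

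Net benefit is λΔE − ΔC, with λ the willingness to pay. The program variables come from operating data and are independent of which children were sampled in Phase 2. Varying the Phase 2 effects and times therefore adds a variance term, which cannot be negative. Leaving it out can only narrow the range.

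**Step 3. Size**

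Let k be λ divided by the point ICER. The net-benefit SE, relative to its cost-only value, is √[1 + (k × CV_effect/CV_cost)²]. Here CV_effect = 0.1112/0.20 = 0.556. The cost CV and k are assumptions, since the documents give neither.

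| k | Cost CV 10% | 20% | 50% | 100% |
|---|---|---|---|---|
| 0.5 | 2.95 | 1.71 | 1.14 | 1.04 |
| 1 | 5.65 | 2.95 | 1.50 | 1.14 |
| 2 | 11.2 | 5.65 | 2.44 | 1.50 |

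The multiplier runs from negligible to large, so no single value can be given.

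**Step 4. Behaviour of the ratio**

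Exact binomial enumeration at 31 per arm:
- 82% v 62%: the observed difference is zero with probability 0.023 and negative with probability about 0.026, so about 5% of draws give no usable ratio.
- 82% in both arms, matching the hypothesis for VR against mock MRI: zero with probability 0.132 and negative with probability (1 − 0.132)/2 = 0.434. At 28 per arm these are 0.139 and 0.431.

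**The case against.** The strongest reply is that silence is being read as exclusion. The plan never says that nothing else will be varied, section 4.5 is an outline, and the study question calls the ratio potential and refers to known limitations. A reader might infer that the plan rules out effect uncertainty; the text does not go that far. What stands is that the plan names the varied inputs and their data source, Phase 2 effects appear in neither, and no other section supplies them. The caveat about limitations does not put effect uncertainty into the reported range.

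Second, the sizes are borrowed. The 82% and the 20% concern child life preparation, the 31 per arm is a stated minimum, availability-based allocation need not give equal arms, and the anxiety and length-of-stay ratios are not quantified here. This is fair. A reader might take a figure such as 5.65 as an estimate of the understatement; the documents do not support that, as the table shows.

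Third, the missing map from status quo and control to arms is a separate reporting gap. The question "What is the cost-effectiveness of current interventional strategies" suggests that several comparators are intended. This too is fair: on its own it is missing detail. It matters here because the mock MRI comparison is the one in which the ratio is least stable.

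Fourth, resampling within arm would not make the interval complete, because section 4.4 concedes that allocation is only partly random. This stands and is taken into the fix.

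**Conclusion.** The point holds. Followed as written, the plan gives a range of cost-effectiveness that omits the sampling error of the Phase 2 effect differences, and of the Phase 2 times behind staff costs, so the range will be too narrow. The omission is read directly from section 4.5, and the direction needs only that program variables be independent of Phase 2 sampling.

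The size is not known. Under the borrowed rates, the half-width of the 95% interval for the effect difference (about 22 points) is as large as the assumed 20-point effect. The times are capped at 45 and 20 minutes, and their contribution is not quantified. The 13% and 43% figures for mock MRI assume both arms truly pass at 82%. It should not be inferred that the ICER is unusable against every comparator. Nor should Phase 3 be set aside as a minor exercise, given its place in sections 3.0 and 4.2.

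**What to change.** In the Uncertainty Analysis paragraph of section 4.5:

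1. Add the Phase 2 effects and times to the varied inputs by resampling children within arm, jointly with the program variables. This covers pass rate, anxiety and length of stay alike and keeps each child's time and outcome together.
2. Beside each ICER, report the cost difference and the effect difference with 95% intervals, with incremental net benefit over a range of willingness to pay (or a cost-effectiveness plane). These should be the main output, because resampling does not cure a denominator near zero.
3. Do this for each Phase 2 comparator, booklet and mock MRI, and say which one stands for the status quo and the control.
4. State that the resampling does not cover bias from availability-based allocation, or the step from a mock scan to real sedation rates, so the interval may still be too narrow.

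No new data are needed. The cost is a few sentences, a resampling step in the model, and wider, less favourable intervals. It can be done before Phase 3 starts.
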